5 POTENTIAL RISKS AND BENEFITS OF INVESTIGATIONAL PRODUCT AND STUDY PROCEDURES

5.1 Risks and Benefits Associated with Posiphen or Placebo

There are no benefits to the subjects other than receiving medical and selective cognitive evaluations.

The clinical investigator should advise all potential subjects of the possibility of unexpected side effects and carefully evaluate each person exposed to Investigational Product for possible AEs.

Side effects to placebo are not uncommon but are obviously not due to a pharmacological agent as an industry standard placebo (non-lactose compound) will be provided. The placebo used for the study consists of microcrystalline cellulose which is generally recognized as safe (GRAS), with no known side effects anticipated.

In clinical studies to date, Posiphen has been well tolerated with single doses of 80 mg or less and QID doses of 60 mg. A higher single dose of 160 mg was associated with an increased incidence of nausea and vomiting, potentially cholinergic based side effects, which resulted in the decision not to test higher single doses. Please refer to table below from the single, ascending dose study, which included healthy men and women:

Table 5.4-1: Summary of Adverse Events in More Than One Subject Per Treatment Group (Males and Females Combined) Study AX-PO-101

Body System Adverse Event ^a (Preferred Term)	Number (%) of Patients in Treatment Group (n = 72)						All Posiphen (n = 60)	Placebo (n = 12)
	10 mg (n = 10)	20 mg (n = 20)	40 mg (n = 10)	80 mg (n = 10)	160 mg (n = 10)			
All AEs, mild	2 (20.0)	4 (20.0)	1 (10.0)	3 (30.0)	3 (30.0)	13 (21.7)	2 (16.7)	
All AEs, moderate	1 (10.0)	2 (10.0)	0 (0)	0 (0)	4 (40.0)	7 (11.7)	1 (8.3)	
All AEs, severe	0 (0)	1 (5.0)	0 (0)	0 (0)	0 (0)	1 (1.7)	1 (8.3)	
Gastrointestinal Disorders								
Nausea	0 (0)	2 (10.0) ^b	0 (0)	0 (0)	4 (40.0)	6 (10.0)	0 (0)	
Vomiting	0 (0)	0 (0)	0 (0)	0 (0)	3 (30.0)	3 (5.0)	0 (0)	
General Disorders and Administration Site Conditions								
Feeling hot	0 (0)	2 (10.0)	0 (0)	0 (0)	0 (0)	2 (3.3)	0 (0)	
Investigations								
Heart rate increased	2 (20.0)	1 (5.0)	0 (0)	0 (0)	0 (0)	3 (5.0)	2 (16.7) ^b	
Nervous System Disorders								
Dizziness	1 (10.0)	4 (20.0) ^b	1 (10.0)	3 (30.0)	4 (40.0)	13 (21.7) ^b	3 (25.0) ^b	
Fainting ^c	1 (10.0)	1 (5.0)	0 (0)	0 (0)	0 (0)	2 (3.3)	1 (8.3)	
Vascular Disorders								
Orthostatic hypotension	0 (0.0)	1 (5.0) ^b	0 (0)	0 (0)	0 (0)	1 (1.7) ^b	1 (8.3) ^b	

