6.1 Randomization

Subjects who have signed an informed consent and meet screening eligibility requirements will be randomly assigned to receive 60 mg Posiphen daily or placebo (with an allocation of 5 on Posiphen, 3 on placebo) by a stratified, random permuted blocked treatment assignment method, stratified by site. Following dosing of the initial 8 subjects and review of safety and tolerability, the next dose group will be 60 mg BID Posiphen or placebo (5 on Posiphen, 3 on placebo). Following the dosing of this group of 8 subjects and review of safety and tolerability, the next dose group will be 60 mg TID Posiphen or placebo (5 on Posiphen, 3 on placebo).

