Power estimates for SILK™ studies involving measurements of FSR of Ab40 were determined by analysis of data provided by C2N, Inc., and modeled to evaluate a primary analytic goal of demonstrating a monotonic dose response relationship to Posiphen treatment. Based on a two-sided t-test for the difference between two independent means at a significance level (alpha) of 0.05 and a statistical power of 80% (1-beta), a sample size of 5 subjects in each treatment group (n active = 15) and 9 controls will provide at least 80% statistical power to detect a 27% change in the mean Ab40 FSR. The following table provides estimated power analysis to detect different effect size reductions of FSR Ab40 of 27% with 2-sided alpha and significance set at 0.05, assuming no dropouts during the SILK™ study:

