4.1 Estimated Power Analysis

A sample size of up to 24 subjects (5 randomized to Posiphen and 3 randomized to placebo per treatment group) is planned across 3-6 clinical research centers.

Table 1. Estimated Power Analysis

	n.active= 12	n.active= 15	n.active= 18
n.cont= 8	0.783	0.822	0.848
n.cont= 9	0.812	0.851	0.876
n.cont= 10	0.836	0.874	0.898

This serves as justification for our sample size estimate of 24. We expect that if dropouts are to occur, they will occur before the SILK™ studies at day 23-25 and can be replaced to allow the full sample size of 24 for SILK™ being achieved.

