4.2 Study Populations

- a. **Enrolled Population:** All participants who consented to screening
- b. **Intention To Treat (ITT) Population:** list of all randomized participants
- c. **Modified Intention-to-Treat (mITT) Population:** Randomized participants who took at least one dose of study medication confirmed by compliance assessment and had at least one post randomization study visit
- d. **Per Protocol (completers):** Randomized participants who were
 - i. compliant through Confinement Visit,
 - ii. compliant to with 20% of dose 1 week prior Pre-Confinement, and
 - iii. completed the 36-hour sampling
- e. **Safety Population:** Randomized participants who:
 - i. took at least one dose of drug confirmed by compliance assessment

5 Statistical Analysis

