5.1 Primary Aims

5.1.1 Aim 1

To determine the safety and tolerability of multiple ascending doses of Posiphen on subjects with early AD with up to 23-25 days of daily usage. Safety and tolerability will be summarized using the following tables, listing and figures:

- Vital signs
- Adverse events onset before randomization
- Adverse events onset after randomization
- AE overall
- AE by severity
- MedDRA coded AEs
- Percentage of AEs summarized by SOC
- Number of participants with at least one AE
- Number of AEs summarized by System Organ Class (SOC) and Preferred Terms (PT)
- Serious AEs (SAE) onset after randomization
- Death summary
- Hospitalization summary
- Safety Labs

5.1.2 Aim 2

To determine the PK of Posiphen and its metabolites in plasma and CSF of subjects with early AD treated with QD, BID and TID dosing regimens., samples will be analyzed at baseline time 0 pre first dose then at times 2H, 4H, 8H, 12 H, 16H, 20H and 24H post dose. Further doses are provided every 8 hours. Curves and area under the curve will be constructed for each of the three sequential dose cohorts of 60 mg daily, 60 mg BID, and 60 mg TID.

Standard PK parameters will be calculated for each subject, including AUC, C_{max} , t_{max} , $t_{1/2}$, V_{ss} . Dose-proportionality will be assessed on C_{max} and AUC statistics. Plasma concentrations will be displayed with time series plots including individual and means by dose. PK parameters summarized descriptively (N,

[figure not shown]
mean (SD) and 95% CI, median, min, max, and geometric mean (%CV) as appropriate) by each dose regimen. Accumulation ratio will be determined. CSF levels will be evaluated by dose levels and correlated where possible to blood levels.

The Charles River Lab in Montreal will analyze PK of Posiphen and its metabolites in Plasma and CSF. This will include Posiphen, N1-Desmethyl Posiphen (Phenserine) and N8-Desmethyl Posiphen (Phenserine). Phenserine is an enantiomer of Posiphen. The chromatographic assay used does not distinguish between the two enantiomers, so these metabolites represent the total amount of both.

5.1.3 Aim 3

To assess the PD effects on the FSR of Ab 40 using the SILK™ technique with multiple doses of Posiphen.

The schema for evaluating the Fractional Synthesis and Clearance Rate, the Absolute Synthesis and Clearance and Area under the concentration curve are presented in **Figure 1**.

The analytic techniques to calculate these values are undertaken by C2N.

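### SAP 5.1.1 tabulates adverse events by SOC and PT in events only, so no listed output is specified to give the share of participants with a given event in each dose group

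*SAP*

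**What the plan says.** SAP 5.1.1 (Aim 1, safety and tolerability, a primary aim) is a list of output titles. Two of them name SOC or PT:

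- "Percentage of AEs summarized by SOC": a percentage by SOC only, with no stated denominator.
- "Number of AEs summarized by System Organ Class (SOC) and Preferred Terms (PT"): a count of events.

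Between them stands "Number of participants with at least one AE", the only AE item worded in participants. It has no SOC or PT breakdown. Three other titles (AEs overall, AEs by severity, MedDRA-coded AEs) state no unit. The section names no columns and gives no rule for repeat events in one participant. SAP 4.2 defines a Safety Population of randomized participants who "took at least one dose of drug confirmed by compliance assessment", but 5.1.1 does not tie the AE tables to it.

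The arm sizes come from "A sample size of up to 24 subjects (5 randomized to Posiphen and 3 randomized to placebo per treatment group") in SAP 4.1 and "a sample size of 5 subjects in each treatment group (n active = 15) and 9 controls" in SAP section 4. Protocol 6.1 gives the same split, "with an allocation of 5 on Posiphen, 3 on placebo". Protocol 6.3 promises a comparison of AE frequencies between participants across three groups, without saying whether frequency means events or people, or which three groups are meant.

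**The concern.** The safety question here is how many people at each dose get a given event. Protocol 6.3, 14.2 and Appendix 5 single out additive cholinergic events in participants who also take a cholinesterase inhibitor. Protocol 3.2 names dizziness, headache and nausea/vomiting as the most common events in the earlier multiple-dose study. Answering the question needs a participant numerator and an arm denominator for each term.

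An event count mixes three things: how many people were affected, how often each was affected, and how many people were in the arm. With arms of 5, 9 and 15, the last of these alone moves the numbers substantially. Arm sizes may also drift from plan, because Protocol 6.3 provides for replacing participants who do not tolerate drug and lets the DSMB change the allocation. Counts without N then become harder still to read.

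**Working it through.** **Inputs from the documents.** Three cohorts of 5 Posiphen and 3 placebo (SAP 4.1, Protocol 6.1): 3 × 5 = 15 active, 3 × 3 = 9 placebo, 15 + 9 = 24. This reproduces the stated total of 24 and the 15 and 9 used in SAP section 4.

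**Assumptions, not in the documents.** The same true risk p in every arm, taken as 10% to 40%.

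**1. Expected event counts at equal risk.** If the mean number of events per person is m in every arm, the expected count in an arm of size n is n × m, and m cancels in the ratio.

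- Pooled Posiphen against pooled placebo: 15m / 9m = 1.67, a false 67% excess on drug.
- Within one cohort: 5m / 3m = 1.67, the same.
- One dose arm against pooled placebo: 5m / 9m = 0.56, a false 44% deficit on drug.

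**2. How often the comparison points each way.** Take one event per affected person, X ~ Binomial(n1, p) and Y ~ Binomial(n2, p). Counts compare X with Y; percentages compare X/n1 with Y/n2. The exact probabilities that the Posiphen figure is higher / lower (the rest are ties) are:

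| Comparison | p | Raw counts | Participant % |
|---|---|---|---|
| 15 v 9 | 10% | 0.52 / 0.22 | 0.49 / 0.43 |
| 15 v 9 | 20% | 0.64 / 0.19 | 0.50 / 0.48 |
| 15 v 9 | 40% | 0.79 / 0.11 | 0.48 / 0.47 |
| 5 v 9 | 10% | 0.19 / 0.44 | 0.34 / 0.44 |
| 5 v 9 | 20% | 0.19 / 0.57 | 0.42 / 0.53 |
| 5 v 9 | 40% | 0.13 / 0.72 | 0.48 / 0.52 |

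Counts lean towards an apparent drug excess in the pooled comparison and towards an apparent deficit for a single dose arm. Percentages are close to neutral at 15 v 9. At 5 v 9 they keep a smaller lean, because five people give few possible values.

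**3. The percentage of AEs.** The result depends on the missing denominator.

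- If it is all AEs in the same arm, the 5:3 allocation does not shift it, but it is a share of events and not a risk. For example, 4 nausea events out of 8 AEs is 50%; with the same 4 nausea events and 16 AEs in total it is 25%.
- If it is all AEs in the trial, equal risk gives expected shares of 15/24 = 62.5% and 9/24 = 37.5%, a ratio of 1.67 again.

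**4. Repeat events (an invented example).** One of 5 participants in a dose arm has 6 vomiting AEs; two of 9 placebo participants have 1 each. Events are 6 against 2, a ratio of 3. Participants are 1/5 = 20.0% against 2/9 = 22.2%, almost the same.

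**The case against.** **The list holds titles, not table shells.** The MedDRA-coded output may be meant as a participant table by SOC and PT, and the percentage by SOC may be meant as a percentage of participants. Both are possible. Nothing in the SAP requires either, and the one title that names PT is worded in events.

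**A reader might infer that the safety tables are wholly event-based.** They are not: participants with at least one AE are listed overall. The gap is at SOC and PT level.

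**A reader might infer that the tables would systematically make the drug look worse.** The documents do not support this. That direction holds for the pooled or within-cohort comparison. It reverses for one dose arm against pooled placebo, which is a natural layout in an ascending-dose trial, and the SAP does not fix the layout. The percentage by SOC, on a within-arm denominator, is not affected by allocation at all.

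**Small numbers do much of the damage.** This stands. Participant percentages are also unstable at 15 v 9: under the same binomial model with p from 20% to 40%, Posiphen shows at least twice the placebo percentage in about 14% to 24% of equal-risk trials, counting those with no affected placebo participant. The change removes the effect of arm size and of recurrence; it does not make 24 people precise.

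**Repeat events dominating an arm is a possibility, not a forecast.** The documents give no recurrence rates. Two places show that it is not far-fetched: Appendix 5 grades vomiting by episodes in 24 hours, and the footnote to the earlier single-dose table in Protocol 5.1 says that one subject may contribute several separately counted AEs. That table is nevertheless headed "Number (%) of Patients in Treatment Group", so its unit is itself not clear-cut.

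**The three groups in Protocol 6.3 may be the three dose cohorts**, each with its own placebo participants. It should not be called a miscount of arms; it needs only to be made explicit.

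**Dose escalation rests on DSMB review, and the tables could be rerun later from the AE records.** True. The point concerns the pre-planned report of a primary aim, not participant protection during the trial.

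**Conclusion.** The point holds at SOC and PT level. As written, SAP 5.1.1 specifies no output giving the number and percentage of participants with a given type of event by treatment group. The event counts that it does specify are misleading at equal per-person risk, by an expected factor of 1.67 for pooled Posiphen against pooled placebo or within a cohort, and 0.56 for one dose arm against pooled placebo. These ratios follow from the planned arm sizes and equal per-person event rates alone. The probabilities in the working rest on assumed risks of 10% to 40% and one event per affected person, and the vomiting example is invented. The documents do not support a claim that the tables favour one side in general, or that the safety reporting contains no participant-level item. This is an improvement to make before analysis at almost no cost, and it does not invalidate the trial.

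**What to change.** In SAP 5.1.1, replace the two SOC/PT items with one table specification:

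- Population: the Safety Population of SAP 4.2; AEs with onset after randomization.
- Content: n/N (%) of participants with at least one event, by SOC and PT, each participant counted once per term.
- Columns: pooled placebo, 60 mg QD, 60 mg BID, 60 mg TID, all Posiphen.
- Event counts beside each n/N (%), so that recurrence stays visible.

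In Protocol 6.3, state that the AE comparison uses these same columns. Counting each participant at worst severity, and exact confidence intervals for the Posiphen minus placebo difference in common terms, are optional additions.

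The cost is a few lines of SAP text, one clarifying sentence in Protocol 6.3 and revised table shells. The AE case report forms (Protocol 14.1) already supply the data.

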Because a substantial proportion of the adverse events observed in AD participants treated with cholinesterase inhibitors appear to reflect the cholinomimetic properties of molecules in this

class, Posiphen's highest tolerated dose is determined by the levels of the N1-norposiphen in blood and brain.

While the $t_{1/2}$ of Posiphen in plasma was 5 hours as seen in the SAD and MAD studies, the $t_{1/2}$ in CSF/brain was longer than 12 hours. Concentrations of Posiphen in the brain, extrapolated from blood and CSF, were 8 times higher than in plasma. 10 days of treatment with Posiphen normalized CSF levels of Soluble Amyloid Precursor Protein (sAPP) and tau, reduced α SYN and a series of inflammatory markers. The concentration and persistence of Posiphen in the brain suggest that much lower doses of drug administered once daily could achieve the desired pharmacological effect.

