6.4 PK Analysis

Plasma concentration-time data will be analyzed by non-compartmental methods using WinNonlin version 6.2.1 or greater. Calculations will be based on the actual sampling times recorded during the study. Only the subjects receiving Posiphen will be included in the PK analysis. From the plasma concentration-time data, the following PK parameters will be determined, as data permit: Area under the curve (AUC) τ , AUC $_{0-\infty}$, C_{max}, t_{max}, t $_{1/2}$, eff, V_{ss}, C τ , AR, and CL.

Dose-proportionality may be assessed on C_{max} and AUC τ as appropriate. Serial pre-dose trough concentrations C τ will be assessed for the attainment of steady-state.

The focus of the PK analysis will be to characterize the preliminary PK of Posiphen. Plasma concentration-time data for Posiphen will be listed and summarized descriptively (number of subjects (N), mean, median, standard deviation (SD), minimum (min), and maximum (max)) and graphically presented. PK parameters will be listed and summarized descriptively (N, mean, median, SD, min, max, and 95% CI) by each dose regimen. Also, a plasma/CSF comparison of the Posiphen PK will be conducted.

In addition, geometric means and between-subject coefficients of variation (CV) will be calculated for AUC τ , AUC $_{0-\infty}$, C_{max}, t_{max}, t $_{1/2}$, eff, V_{ss}, C τ , AR, and CL. All PK analyses will be performed by the ADCS Biomarker Core.

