12.2.3 Plasma for Biomarkers and Pharmacokinetics

Plasma samples will be collected at screening visit and during the confinement visit every 2 hours for analysis of AD biomarkers (e.g., A β 40 & 42 and exploratory biomarkers), cholinesterase inhibition, and drug level analyses.

Biomarker and PK analyses at the screening visit will be performed on the 10 ml EDTA plastic tube whose collection is described in Section 12.2.2.

In addition, 10 ml of blood will be collected in a uniform fashion into 10mL lavender top EDTA tubes at hours 0, 2, 4, 6, 8, 10, 12, 14, 16, 18, 20, 22, 24, 26, 28, 30, 32, 34, and 36 during the confinement visit. Once blood is collected, it should be centrifuged at 1500 x g for 10 minutes at room temperature. 2 ml of plasma should be aliquoted into 2.0 ml freezer tubes, frozen at -80°, and shipped overnight on dry ice to the ADCS Biomarker Core.

At the last collection (36 hours), an extra 9mL of whole blood should be sent to the central lab for metabolic panel and CBC/Diff.

Plasma samples will be banked in the biospecimen repository of the ADCS Biomarker Core for future research studies; access to samples will be granted according to SOPs established by the ADCS Biomarker Core.

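### SAP 5.1.2 promises an accumulation ratio, Vss and per-subject half-life that the PK sampling cannot fully support, and its thinned time grid biases AUC differently by regimen

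*SAP*

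**What the plan says.** SAP 5.1.2 promises: "Standard PK parameters will be calculated for each subject, including AUC", followed by Cmax, tmax, half-life and Vss. It then adds "Accumulation ratio will be determined", with no formula or reference profile. Dose-proportionality is to be judged on Cmax and AUC; no AUC interval is named.

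The sampling times are "baseline time 0 pre first dose then at times 2H, 4H, 8H, 12 H, 16H, 20H and 24H post dose". The next sentence reads "Further doses are provided every 8 hours".

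The protocol sets the frame:

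- **Occasions (12.2.3):** "Plasma samples will be collected at screening visit and during the confinement visit every 2 hours". Confinement sampling runs from 0 to 36 h.
- **Timing (9.5):** admission is 21-23 days (± 2) after the first dose.
- **Route and capsules (7.2):** oral only, three capsules a day in every group, of which one, two or three are active.
- **Capsules in confinement (9.5.2):** at 0, 8, 16, 24 and 32 h.
- **Parameters (6.4):** "the following PK parameters will be determined, as data permit". The list includes AUCtau, AUC0-infinity, effective half-life, Vss, accumulation ratio and CL, all from plasma. Dose-proportionality is tied to Cmax and AUCtau.

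**The concern.** An observed accumulation ratio compares a steady-state profile with a first-dose profile, and no first-dose profile is planned. A true Vss needs an intravenous reference, and there is none. A half-life for each subject needs enough points over a long enough stretch before the next active dose, which the TID schedule does not provide. The protocol's condition that parameters depend on the data was not carried into the SAP.

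AUC matters more for the conclusions. It feeds dose-proportionality and the PK/PD analyses in SAP 5.1.3 and 5.2.2, yet its interval is undefined. It is also to be computed from a grid with 4 h gaps after 4 h, while doses recur every 8 h. The later absorption peaks fall inside those gaps, so the more active doses a regimen has, the more of its AUC is missed.

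**Working it through.** The documents state no value for these quantities in this trial, so there is no figure to reproduce.

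**Inputs.** Protocol 3.2 gives plasma half-life of 4.104 h (60 mg, repeat dosing) and 5.23 h (60 mg, single dose), tmax of 1.2-1.5 h, and a half-life that "in CSF/brain was longer than 12 hours". The SAP times are 0, 2, 4, 8, 12, 16, 20 and 24 h. Assumptions: one-compartment oral model at steady state, linear kinetics, tmax 1.35 h; the QD active capsule at 0 h; BID active capsules at 0 and 8 h or at 0 and 16 h. The documents do not say which capsules are active.

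**1. Accumulation ratio.** Observed AR = AUCtau at steady state / AUCtau after the first dose. The denominator is never measured. Only a predicted value is possible:

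AR = 1/(1 − 2^(−tau/t½))

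At t½ = 4.104 h:
- tau 24 h: 1/(1 − 0.017) = 1.02
- tau 12 h: 1/(1 − 0.132) = 1.15
- tau 8 h: 1/(1 − 0.259) = 1.35

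At 5.23 h the values are 1.04, 1.26 and 1.53. The BID value assumes a 12 h interval, which does not occur on the 8-hourly confinement grid.

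**2. Volume.** Oral data give volume divided by bioavailability, that is, an apparent volume.

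**3. Plasma half-life.** Span in half-lives = (last − first usable time)/t½. The 95% ranges come from 20,000 simulated log-linear fits per setting, with an assumed log-scale error SD of 0.20.

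| Regimen | Usable points | Span | Range, true 4.10 h | Range, true 5.23 h |
|---|---|---|---|---|
| QD | 6 (4-24 h) | 20/5.23 to 20/4.104 = 3.8-4.9 | 3.6-4.8 h | 4.5-6.3 h |
| BID | 4 | 12/5.23 to 12/4.104 = 2.3-2.9 | 3.3-5.5 h | 3.9-7.8 h |
| TID | 3 (2, 4, 8 h) | 6/5.23 to 6/4.104 = 1.15-1.46 | 2.7-9.2 h | 3.1-16.2 h |

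**4. AUC0-24.** Linear trapezoid as a fraction of true AUC, for t½ 4.104 to 5.23 h:

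| Regimen | SAP times | Every 2 h |
|---|---|---|
| QD | 0.93-0.94 | 0.91-0.93 |
| BID | 0.84-0.87 | 0.91-0.93 |
| TID | 0.82-0.85 | 0.91-0.93 |

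Under exact proportionality the true TID:QD ratio of AUC0-24 is 3. The SAP grid would show 3 × 0.817/0.927 = 2.64 at 4.104 h and 3 × 0.848/0.936 = 2.72 at 5.23 h, an apparent shortfall of 9-12%. With 2-hourly samples the bias is the same in every regimen and cancels from the ratio. The QD figure depends on the active capsule being at 0 h; at 8 or 16 h its peak would also fall in a 4 h gap.

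**5. Time 0.** Modelled pre-dose concentration relative to Cmax is 2-5% in QD, 9-36% in BID and 35-43% in TID. It is a trough, not a drug-free baseline.

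**The case against.** The strongest reply is that Protocol 6.4 describes preliminary, descriptive PK, makes the parameter list conditional on the data, and names AUCtau for dose-proportionality. Dose escalation rests on safety review, not on these parameters. All of that is true. It limits the consequences, but the SAP is the document the analyst will follow, and it kept neither the condition nor the tau.

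Four stronger readings are tempting and are not supported:

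- **Hour 0 treated as the trial's first dose.** A reader might infer this from "samples will be analyzed at baseline time 0 pre first dose", and conclude that the accumulation ratio would come out at 1.00 in every regimen. The following sentence on further doses fits the confinement visit, and SAP 5.2.2 treats day 21 time 0 as the trough. The label is loose, but it does not establish a wrong analysis. With no formula given, no value of the ratio follows from the text.
- **Dose-proportionality distorted by AUC0-infinity.** Neither AUC0-infinity nor CL appears in SAP 5.1.2, and the protocol judges proportionality on AUCtau.
- **An impossible CSF half-life.** The protocol derives its listed parameters from plasma. The SAP says only that CSF levels will be evaluated by dose and correlated with blood where possible. No CSF half-life is clearly promised.
- **Aim 2 as meaningless.** Interval AUC, trough, observed Cmax and tmax, and the plasma/CSF comparison all remain available.

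**Conclusion.** The concern holds in a limited form and should be corrected before the PK analysis. That an observed accumulation ratio and a true Vss are unobtainable follows directly from the sampling occasions and the oral route, without any model. That half-life is unreliable per subject in TID rests mainly on the short span; the simulated ranges depend on the assumed 0.20 error.

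The AUC effect is moderate: under the stated model, a proportional drug would look 9-12% short of proportional from QD to TID. Its size depends on linear one-compartment kinetics, on which capsules are active and when, and on use of the linear trapezoid. Protocol 3.2 reports disproportionate Cmax across 20, 40 and 60 mg doses, so linearity is itself uncertain. The direction comes from the wide gaps around the later doses, and the remedy uses samples already drawn.

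**What to change.** In SAP 5.1.2:

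1. Drop the accumulation ratio, or report it as model-predicted, 1/(1 − exp(−k·tau)), and state that it assumes linear kinetics with the same k across regimens.
2. Replace Vss with apparent volume, Vz/F.
3. Replace the bare AUC with AUCtau,ss and AUC0-24,ss, matching the AUCtau in Protocol 6.4 for dose-proportionality.
4. Report half-life only where stated criteria for number of points and span are met.
5. Relabel time 0 as the day 21-23 steady-state pre-dose sample, in line with SAP 5.2.2.
6. Assay the 2-hourly samples already collected, and analyse by actual active-dose times after unblinding.

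The QD and BID regimens must also be reconciled with the 8-hourly capsule schedule in Protocol 7.2 and 9.5.2 and SAP 5.1.2, so that tau is defined for each regimen. This is a request to align the passages, not a proposal for any schedule.

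The cost is SAP wording plus extra assays. No additional visit or sample is needed.
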